# c. Secondary Outcome Measures

- i. Waivered PCC prescribing and referral behavior. As an exploratory outcome, we will gather the rate of MOUD, naloxone, and opioid prescriptions and referrals to waivered clinicians (primary care and specialty addiction medicine) among eligible patients in the 12 months prior to the study and during the 6-month follow-up period to determine whether the stigma reduction and/or control training affected change in prescribing behavior.
- ii. PCC waiver status. In addition to intentions to get waivered, change in waiver status will be collected as an exploratory outcome. A list of waivered PCCs will be pulled from HP administrative data to determine if additional PCCs became waivered during the follow-up period.
- iii. *PCC willingness to work with people with OUD.* PCCs will report on their willingness to work with people with OUD using 3 items adapted from the Drug Problems Perceptions Questionnaire.  PCCs will respond to each item using a 5-point Likert-type scale ranging from 1 (*strongly disagree*) to 5 (*strongly agree*). One item is reverse scored ("I would enjoy my job more if I could stop working with patients with opioid use disorder") and the items will be averaged for a total score, with higher scores corresponding to greater willingness to work with people with OUD.
- iv. PCC opioid treatment outcome expectancies. Treatment outcome expectancies will be assessed using two items developed for this study. First, PCCs will rate the extent to which they believe available treatments are effective for treating OUD on a 4-point Likert-type scale ranging from 1 (not at all effective) to 4 (very effective). The second item will ask PCCs to rate the extent they believe patients will comply with those treatments on a 4-point Likert-type scale ranging from 1 (not at all likely) to 4 (very likely). Items will be analysed separately.
- v. PCC perceptions of the training and the Opioid Wizard tool. In the initial survey, PCCs will provide feedback on the training in four questions, including their perception of the usefulness and ease of use of the training and their intentions to use the Opioid Wizard tool. At the 3-month follow-up survey, these questions will be replaced with items specifically about Opioid Wizard, not the training, to assess likelihood of recommending Opioid Wizard to colleagues, frequency of using Opioid Wizard, Opioid Wizard ease of use, and intention to use Opioid Wizard in the future.

#### d. Covariates

i. Demographics. PCCs will report on their demographic characteristics, including gender, age, race, ethnicity, and days per week in clinic in the survey. HealthPartners administrative data will be used to determine clinician type (MD/DO, nurse practitioner, or physician assistant).

- **ii.** *Frequency in addressing OUD.* PCCs will report on the frequency with which they typically address OUD in their practice using one item: How often do you treat patients with opioid use disorder? Response options will be on a 5-point Likert-type scale ranging from 1 (*never*) to 5 (*daily*).
- iii. PCC perceived vulnerability to OUD. PCC perceived vulnerability to developing OUD will be assessed using 3 items. PCCs will rate the extent they agree with each statement on a 5-point Likert-type scale ranging from 1 (strongly disagree) to 5 (strongly agree). One item will be reverse-scored ("If I were prescribed opioids, there is a real risk I would become addicted"). Items will be averaged for a total score, with higher scores corresponding to lower perceived vulnerability to OUD.

# I. Post-recruitment retention strategies

- a. Participant retention. To encourage PCCs to complete the training, they will receive up to 4 reminders and will be offered a \$100 incentive. We may also ask clinic leaders to remind PCCs to complete training. Further, PCCs will be offered an additional \$25 incentive for completing the follow-up assessment at 3 months. Direct email communications will be sent to request and remind them about the survey. There may be volunteer bias in those who complete the training; however, this should not compromise internal validity as factors that predict participation should be random across intervention assignment. We will describe differences between completers and non-completers (e.g., gender, PCC type, waiver status, clinic).
- **b. Participant withdrawal.** Participants may withdraw from the study at any time. It is possible that they will not complete the training or the surveys. However, the training and surveys are designed to be short so they do not overburden participants.

# J. Risks, benefits, safety monitoring and adverse events

- a. Risks to participants. This study involves minimal risk. The primary risk to PCCs is the risk of loss of confidentiality. However, the study team will take multiple steps to reduce those risks. First, each PCC will be assigned a unique study identification number. Their identifying information will be stored separately from their study data, and only the study team will have access to any linkage files. Those files will be stored on a secure, HealthPartners server only accessible by the study team, and will primarily be used to provide incentives to participants. Analytic data sets will not include any identifying information.
- b. Benefits. There are no direct benefits to participants in this study. However, the PCCs may find the training useful in helping them navigate Opioid Wizard, which could reduce frustration in learning a new EHR platform. One potential benefit is the knowledge of whether a training delivered via an online platform can incorporate patient narratives and ultimately reduce stigma among PCCs toward people with opioid use disorder, which has the potential to increase the availability of treatment in this population.
- **c. Data and safety monitoring.** Given the minimal risk involved in this study, a data and safety monitoring board (DSMB) is not indicated for this study. The parent trial has an independent DSMB appointed by the NIDA CTN that oversees that study.
- **d.** Adverse event reporting requirements. This is a minimal risk study. Adverse events and Serious Adverse events will not be collected in the context of this trial.

#### K. Data collection and management

a. Data collection and management. Recruitment data will be stored in a protected project folder on a secure network drive. Surveys will be collected using REDCap, a secure data management software that stores data on internal HealthPartners servers. PCCs will get a link to the survey immediately after completing the training and will be instructed to fill out the survey in order to receive compensation for their time. PCCs will directly answer survey questions within the REDCap platform. For the follow-up survey, PCCs will receive an email and reminders at the time they are due for their follow-up. The email will have a link to the survey and PCCs will be able to directly answer the questions in the REDCap platform. Survey data will be accessed by study staff to determine which PCCs are eligible for incentives.

Opioid Wizard use will be captured passively through the Opioid Wizard system, and prescriptions, referrals, and patient characteristics will be captured through the EHR. PCC Waiver status will be extracted from HealthPartners administrative data at the end of the study follow-up period. Data will be extracted by the study team and stored securely on the HealthPartners secure internal server. Patient data will be identified with a random unique identifier generated by the Wizard platform. The study programmer will use that information to pull data from the EHR. No MRNs or patient IDs will be retained in an analytic dataset.

- **b. Quality control.** Survey responses will be directly entered by participants into REDCap survey software. We will program REDCap to minimize non-viable or non-allowable responses (e.g., limiting age to integers between 18 and 100). Participants will only be allowed to choose one Likert-type response on scale items. In addition, participants will be prompted to complete items that do not have a response, but will be allowed to leave them blank if they choose to do so.
- c. Progress reports. During study recruitment phases (initial training and follow-up survey), we will use REDCap reports to generate study completion rates and to prompt reminders to complete the training and surveys. The team will review the reports to determine if other strategies (e.g., reaching out to clinic leadership) are needed to boost recruitment and retention.

# L. Sample size

There are 449 PCCs in the 30 clinics being considered for randomization to the parent study, COMPUTE 2.0, with an average of 15 per clinic (range 4-36). To the extent that the parent study will seek balance between treatment arms in clinic size, and by extension number of PCCs, we estimate that 225 PCCs will be in intervention clinics and eligible for this study. We have estimated power for PCC participation rates of 50%, 65%, and 80% with equal numbers of PCCs per arm. Approximately 93% of PCCs at HP are not waivered, which would reduce available sample sizes for H1b and H1c to 208 PCCs. The power analysis was calculated using G\*Power 3.1 and determined the minimal detectable standardized effect between groups for each outcome given available sample size,  $\alpha_2$  = .05, and desired power (see Table 1). Given these assumptions, we will have the ability to detect moderate differences (80% power: d = 0.42-0.55; RR=1.28-1.58) between the groups.

For Aim 2, the regression models will include PCCs in both arms and up to 4 covariates. Given sample size,  $\alpha_2$  = .05, and desired power, we will have adequate power to detect small effects for H2a (80% power:  $f^2$  = 0.05-0.08) and moderate effects for H2b (80% power: RR=1.29-1.60).

Table 1. Minimal detectable	Table 1. Minimal detectable standardized effects based on PCC						
participation rate and desired power.							
PCC participation= 50% 65% 80%							

	112 F	PCCs	146 F	PCCs	180 F	PCCs	
ро	wer =	0.80	0.90	0.80	0.90	0.80	0.90
H1a: OUD Stigma	d	0.49	0.57	0.47	0.54	0.42	0.49
H1b, H1c: Intentions	d	0.55	0.64	0.48	0.56	0.44	0.51
H1d: CDS Use: 30%	RR	1.58	1.69	1.50	1.59	1.44	1.52
50%	RR	1.44	1.51	1.38	1.44	1.34	1.39
70%	RR	1.36	1.43	1.31	1.37	1.28	1.33
H2a: Intentions	f 	0.08	0.10	0.06	0.08	0.05	0.06
H2b: CDS Use: 30%	RR	1.60	1.71	1.52	1.61	1.46	1.54
50%	RR	1.45	1.53	1.39	1.46	1.35	1.41
70%	RR	1.37	1.44	1.32	1.38	1.29	1.34
Note. Cohen's d = d; Co	hen's	$f^2 = f^2; I$	Rate ra	tio = RF	₹.		

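### Table 1 understates the detectable effect for H1a (stigma) at 50% participation: 112 PCCs give d = 0.53 and 0.62, not 0.49 and 0.57

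*Combined protocol and SAP*

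**What the plan says.** Section L (Sample size) starts from a fixed pool: "we estimate that 225 PCCs will be in intervention clinics and eligible for this study". It then states: "We have estimated power for PCC participation rates of 50%, 65%, and 80% with equal numbers of PCCs per arm". Table 1 gives these three scenarios as 112, 146 and 180 PCCs. The calculation used G*Power 3.1 with alpha of 0.05 (the subscript 2 is read as two-sided) and "determined the minimal detectable standardized effect between groups for each outcome given available sample size".

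For the intention outcomes the pool is smaller: "Approximately 93% of PCCs at HP are not waivered, which would reduce available sample sizes for H1b and H1c to 208 PCCs".

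The row "H1a: OUD Stigma" prints d = 0.49 / 0.57 (80% / 90% power) for 112 PCCs, 0.47 / 0.54 for 146 and 0.42 / 0.49 for 180. The H1b/H1c row prints 0.55 / 0.64, 0.48 / 0.56 and 0.44 / 0.51. The text summarises d at 80% power as 0.42 to 0.55.

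No covariate, attrition or clustering adjustment is stated for the H1a calculation. Covariates enter section L only for the second aim: "For Aim 2, the regression models will include PCCs in both arms and up to 4 covariates".

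**The concern.** The table is inconsistent on its face. At 80% power, going from 146 to 112 PCCs (34 fewer) raises the H1a detectable d by only 0.02, from 0.47 to 0.49. Going from 112 PCCs (H1a) to about 104 (H1b/H1c), only 8 fewer, raises it by 0.06, from 0.49 to 0.55. At 65% and 80% participation the two rows differ by 0.01 to 0.02; at 50% they differ by 0.06 to 0.07.

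Stigma is one of the primary outcomes (section H.b and section M) and the direct target of the training. It is measured by a survey after voluntary training, so its sample size depends on participation. The 50% column is therefore where sensitivity is most in doubt. As printed, it suggests that falling from 65% to 50% participation costs H1a almost nothing. Section K.c has the team review completion rates to decide whether more recruitment effort is needed, and a reader using Table 1 for that purpose would be misled.

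**Working it through.** **Inputs (all from section L).** Two-sided alpha 0.05; equal arms; 225 eligible PCCs, so 112, 146 and 180 PCCs at 50%, 65% and 80%, or n = 56, 73 and 90 per arm. For H1b/H1c: 208 × 0.50 = 104, 208 × 0.65 = 135.2 and 208 × 0.80 = 166.4; even totals of 104, 136 and 166 are used below.

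**Method.** Two-sample t test, df = 2n − 2, noncentrality λ = d·√(n/2). Power = P(|T| > t(0.975, df)), where T is noncentral t with parameter λ. Solve for d at power 0.80 and 0.90.

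**Reproducing the plan's figures**

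| Row | Total PCCs | Printed d (80% / 90%) | Recomputed d (80% / 90%) |
|---|---|---|---|
| H1a | 180 | 0.42 / 0.49 | 0.420 / 0.486 |
| H1a | 146 | 0.47 / 0.54 | 0.467 / 0.540 |
| **H1a** | **112** | **0.49 / 0.57** | **0.534 / 0.618** |
| H1b/H1c | 166 | 0.44 / 0.51 | 0.438 / 0.506 |
| H1b/H1c | 136 | 0.48 / 0.56 | 0.484 / 0.560 |
| H1b/H1c | 104 | 0.55 / 0.64 | 0.555 / 0.642 |

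All the d cells reproduce to within 0.01 except the two for H1a at 112 PCCs. The H2a row also reproduces, with one tested term among five predictors: f² = 0.077 / 0.103 at 104, 0.059 / 0.079 at 135 and 0.048 / 0.064 at 166, against printed 0.08 / 0.10, 0.06 / 0.08 and 0.05 / 0.06. The rate-ratio rows (H1d, H2b) were not recomputed.

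**Hand checks.** The normal approximation d = (z(0.975) + z(power))·√(2/n) with n = 56 gives:

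- 80% power: (1.960 + 0.842) × 0.189 = 0.53
- 90% power: (1.960 + 1.282) × 0.189 = 0.61

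Detectable d also scales as 1/√N. Starting from the recomputed 146-PCC values, √(146/112) = 1.142, so 0.467 × 1.142 = 0.533 and 0.540 × 1.142 = 0.617.

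**Power at the printed effects, 56 per arm**

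- d = 0.49: λ = 0.49 × √28 = 2.59, power 72.9% (not 80%); type II error 27.1% rather than 20%.
- d = 0.57: λ = 0.57 × √28 = 3.02, power 84.8% (not 90%).
- Allowing for rounding of the printed d (0.485 to 0.495; 0.565 to 0.575), power is 72.0% to 73.8% and 84.2% to 85.5%.

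**Sample size that the printed effects require.** d = 0.49 at 80% needs 132.7 PCCs (132.7 / 225 = 59.0%). d = 0.57 at 90% needs 131.3 (131.3 / 225 = 58.4%).

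**Other explanations tried**

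- A one-sided 0.05 test at 112 PCCs gives 0.473 / 0.557, which does not match.
- Covariate adjustment would need R² = 1 − (0.49 / 0.534)² = 0.16, or 1 − (0.57 / 0.618)² = 0.15. None is stated, and it would have to apply to these two cells and to no other H1a cell.
- 132 PCCs (66 per arm) gives 0.491 / 0.569, which rounds to both printed values. Entering 66 for 56 would explain them, but that is inference; the documents do not say how the values arose.

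**The case against.** The strongest reply is that nothing rests on these cells. The sample size was not derived from Table 1: all eligible PCCs in the 15 intervention clinics are randomized, and the table only describes what that fixed pool can detect. The corrected 0.53 lies inside the text's range of 0.42 to 0.55, whose upper end comes from H1b/H1c, so the claim to detect moderate effects is untouched. This stands and limits the consequence. It does not make the cells right.

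Three further points are fair. The documents set no hierarchy among the primary outcomes, so H1a is the first listed and no more. Table 1 fixes power and solves for d, so the primary error is in d (0.04 to 0.05 too small); the power figures re-express it. And the documents do not show which input went wrong, so the authors may hold a sample size or adjustment that they did not report.

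Damage in reading the PDF is an unlikely explanation: the two values form a coherent pair that fits one sample size of about 132.

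**Conclusion.** The two H1a cells under 112 PCCs are wrong on the plan's stated inputs. The detectable d is 0.53 at 80% power and 0.62 at 90%, against the printed 0.49 and 0.57. Power at the printed effects falls short by 7.1 points (80 − 72.9) and 5.2 points (90 − 84.8). This rests on a two-sided 0.05 t test, equal arms, 112 analysed PCCs and no covariate or clustering adjustment, which is the reading that reproduces the other d cells. The error is confined to two cells among the d and f² rows; no claim is made about the rate-ratio rows. It should be corrected because it misstates the sensitivity of a primary outcome in the least favourable scenario, but it does not alter the design or the plan's overall statement on power.

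**What to change.** In Table 1, row H1a, under 112 PCCs, replace 0.49 with 0.53 (80% power) and 0.57 with 0.62 (90% power). If the printed values came from a different sample size or from an assumed covariate adjustment, state that input and apply it consistently across the row. The text range of d = 0.42 to 0.55 can stay. The cost is two table cells, with no change to recruitment, randomization or analysis.

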# C. Objectives, Aims, & Hypotheses

In response to NOT-OD-101: HEAL Initiative: Notice of Special Interest (NOSI) regarding the Availability of Administrative Supplements to Support Strategies to Reduce Stigma in Pain Management and OUD and Treatment, this project will evaluate an intervention to reduce stigma in PCCs by integrating stigma reduction training into the Opioid Wizard training. PCCs will be randomized to this novel stigma reduction training, grounded in stigma science, or an attention-control training. The overall goal of this project is to determine whether stigma reduction training reduces PCC stigma, increases intention to get waivered to prescribe buprenorphine or to prescribe buprenorphine if a waiver were no longer required, and ultimately increases the likelihood that PCCs use Opioid Wizard.

Aim 1: To examine whether a PCC training to reduce stigma toward people with OUD, compared to an attention-control training, reduces stigma, increases intention to get waivered, increases intention to prescribe buprenorphine if a waiver were no longer required, and increases the likelihood of using Opioid Wizard.

**H1a:** PCCs who are randomized to stigma reduction training will report less stigma towards patients with OUD compared to PCCs who are randomized to control training.

**H1b:** Among non-waivered PCCs, PCCs who are randomized to stigma reduction training will report greater intention to get waivered to prescribe buprenorphine than PCCs who are randomized to control training.

**H1c:** Among non-waivered PCCs, PCCs who are randomized to stigma reduction training will report greater intention to prescribe buprenorphine for OUD in the next year if a waiver were no longer required than PCCs who are randomized to control training.

**H1d:** PCCs who are randomized to stigma reduction training will use Opioid Wizard at a greater proportion of visits where the PCC is alerted to high risk than PCCs who are randomized to control training.

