# E. Study Population

- a. Participants. Participants will be PCCs who practice at HealthPartners Clinics that have been previously randomized to the intervention arm of the parent study, Opioid Wizard. There will be 15 clinics randomized to receive the Opioid Wizard intervention. There are 225 eligible PCCs in the clinics randomized to the OUD-CDS. All randomized clinicians will be included in the analysis of Wizard use and prescribing and/or referral behavior (in event referrals are made to waivered clinicians).
- b. Inclusion and exclusion criteria. To be eligible for inclusion in this study, a PCC must practice at a study-eligible primary care clinic and be a family physician, general internist or adult-care non-obstetric nurse practitioner or physician assistant. PCCs are study-eligible regardless of whether they are waivered to prescribe buprenorphine.

**Sources or methods of recruitment.** For the parent study, PCCs will have the opportunity to participate in a webinar about general training of the Opioid Wizard tool. This webinar will include information about CDS alerts, printing the PCC and patient priorities, and using the tool within Epic's (EHR) active guidelines. At the end of the webinar, all eligible PCCs in intervention clinics will be notified about the opportunity to participate in additional case-based training on using Opioid Wizard, which they will receive an invitation to complete in their email. Up to three emails will be sent to PCCs from the MyLearning platform inviting them to participate in the training. The email will provide an introduction to the study and the elements of consent. We may also use additional strategies to encourage study participation, including asking clinic leaders to remind their PCCs to complete the training and directly emailing a final reminder before the initial survey closes. See **Appendix A** for recruitment email and **Appendix B** for the consent document. (Subsequent communications have been submitted separately as amendments.)

PCCs who complete the initial training via MyLearning (either the stigma reduction training or the comparison [attention control]) will be emailed a follow-up survey 3 months after they completed the initial training. PCCs will receive up to 4 emails to remind them to complete the follow-up survey. The recruitment email for the follow-up survey is available in **Appendix C**.

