#### H. Outcome assessment

**a.** Timing of outcome assessment. Immediately following training, PCCs will be asked to complete a brief (15-minute) follow-up survey via REDCap, a secure data

management software, to assess self-reported outcomes: stigma, waiver status, and, among non-waivered PCPs, intention to get waivered and intention to prescribe buprenorphine should a waiver no longer be required (see **Appendix D**). In addition, at 3 months following the training, PCCs will be asked to complete a follow-up survey via REDCap, to assess endurance of the stigma training on PCC stigma and intentions (see **Appendix E**). Opioid Wizard use will be pulled from CDS meta-data for each randomized clinician for encounters that are eligible for the Opioid Wizard intervention. PCC prescribing (number of MOUD, naloxone, and opioid prescriptions and the number of unique patients receiving prescriptions) and referral behavior will be extracted from the EHR. We will pull patient demographic information from the EHR to assess the extent to which provider behaviors differ across patient sub-groups, such as racial/ethnic groups, sex, and reason for intervention eligibility.

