- iii. Intentions to prescribe buprenorphine should a waiver no longer be required. Non-waivered PCCs will be asked to rate one question on their intentions to get waivered to prescribe buprenorphine: "If your patient with OUD requested buprenorphine in the next year and a waiver were no longer required, would you prescribe buprenorphine?" PCCs will rate their response on a five-point Likert-type scale ranging from 1 (I definitely would not) to 5 (I definitely would). We have added this question given recent press reports that the federal government is considering no longer requiring a waiver to prescribe buprenorphine for physicians. Even if this potential rule change does not go into effect during this study, press coverage of this potential change could influence clinicians' intent to complete the waiver change (i.e., anticipating that soon it may no longer be required). The addition of this question provides a measure of intent to treat OUD with buprenorphine regardless of the waiver requirements at the time the question is answered. As noted above, moderate-to-large changes in

behavioral intentions are associated with small-to-moderate changes in behavior.

iv. Opioid Wizard Use. High use rates of Opioid Wizard are an important measure of PCC engagement. PCC Opioid Wizard use will be defined as taking action within the CDS tool, such as reviewing relevant chart history, screening for OUD, making a diagnosis, providing a referral or prescribing a medication, printing patient education materials, or prescribing naloxone. The use rates for each PCC for the follow-up period (6 months) will be calculated as the proportion of eligible visits in which Opioid Wizard was used. This provides an objective measure of PCC behavior with little social desirability bias.

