In secondary analysis, we will examine whether self-reported stigma mediates the effect of the intervention on Opioid Wizard use. If the intervention affects Opioid Wizard use (H1d), and stigma is related to Opioid Wizard use (H2b), we will use a product of coefficients approach to quantify how much of the intervention effect is mediated by stigma. In other exploratory analyses, we will examine whether PCCs in the stigma reduction arm prescribe MOUD and /or naloxone to eligible patients at a higher rate than PCCs in the comparison arm, controlling for pre-Opioid Wizard prescribing behavior. We will also examine whether PCCs in the stigma reduction arm prescribe opioids to eligible patients at a lower rate than PCCs in the comparison arm, controlling for pre-Opioid Wizard prescribing behavior. Further, as a follow-up to H1b, we will examine whether PCCs in the stigma reduction arm are more likely to get waivered than control PCCs using a logistic regression framework. To understand how PCC experience with patients at high risk for problems with opioids may have influenced their decision to participate in this study, we will compare PCC prescribing and referral behaviors among PCCs who completed the training to those who did not among all randomized PCCs.

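### Table 1 sizes H1d on training participants (112/146/180) although all randomized clinicians (about 225) are to be analysed, and sizes H2b as a rate ratio although linear regression is planned

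*Combined protocol and SAP*

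**What the plan says.** Section L sets the basis for the whole of Table 1: "We have estimated power for PCC participation rates of 50%, 65%, and 80% with equal numbers of PCCs per arm". Out of an estimated 225 eligible PCCs this gives column heads of 112, 146 and 180, and the same heads serve every row. For H1d the table gives detectable rate ratios at 30%, 50% and 70% use. The text summarises the Aim 1 rows as "Given these assumptions, we will have the ability to detect moderate differences (80% power: d = 0.42-0.55; RR=1.28-1.58) between the groups".

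The H1d analysis set is described elsewhere. Section E, Participants: "All randomized clinicians will be included in the analysis of Wizard use". Section H, Timing of outcome assessment: "Opioid Wizard use will be pulled from CDS meta-data for each randomized clinician". Section M confirms that the randomized set contains PCCs who did not complete training, because it plans a comparison "among PCCs who completed the training to those who did not among all randomized PCCs". H1d itself is worded by randomized arm: PCCs randomized to stigma reduction training "will use Opioid Wizard at a greater proportion of visits where the PCC is alerted to high risk". The measure is a per-PCC use rate, "calculated as the proportion of eligible visits in which Opioid Wizard was used".

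For H2b, section L claims power to detect "moderate effects for H2b (80% power: RR=1.29-1.60"). Section M plans multiple linear regression for both Aim 2 outcomes, Opioid Wizard use included. The open choice of error distribution and link in section M is given for Aim 1 only.

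**The concern.** Participant numbers suit H1a to H1c, which need a completed survey, and H2b, which needs the survey stigma score. H1d needs no survey, since use is captured passively for everyone randomized. Moving from participants to all randomized PCCs does two things at once: it raises N, and it brings in clinicians who received neither training. Table 1 reflects neither, and section L does not say whether its RR is the effect among trained PCCs or among all randomized PCCs.

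For H2b, the effect measure in the power statement cannot come out of the planned model.

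Opioid Wizard use is the one primary outcome that is measured objectively. If H1d is null, readers will use the sensitivity statement to judge what size of effect was ruled out, and the present statement refers to a different set of clinicians. N is fixed by the parent trial, so the issue is what the protocol may say it can detect, not how many PCCs to enrol.

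**Working it through.** **Inputs.** From section L: two-sided alpha 0.05; power 80% and 90%; 225 eligible PCCs; columns of 112/146/180; base use b = 30/50/70%; up to 4 covariates for Aim 2. From section F: 1:1 allocation. The G*Power procedure, predictor distribution and exposure are not reported.

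**Step 1: reproduce the printed H1d row.** Two Poisson set-ups fit it.

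- Standard normal predictor, exposure 1: power = Φ(√N × ln RR / s − 1.96), with s² = 1/(b × exp((ln RR)²/2)). Example at b = 0.30, N = 112, RR = 1.58: ln RR = 0.457, s = 1.733, so 10.583 × 0.457/1.733 − 1.96 = 0.83 and power is 80%.
- 50:50 arm indicator with T visits per PCC: power = Φ(ln RR / √[(2/(N T b))(1 + 1/RR)] − 1.96). T = 3.63 is back-fitted and is not in the documents.

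| Use | Printed, 80% power (N = 112/146/180) | Normal predictor | Arm indicator |
|---|---|---|---|
| 30% | 1.58 / 1.50 / 1.44 | 1.582 / 1.501 / 1.446 | 1.582 / 1.500 / 1.445 |
| 50% | 1.44 / 1.38 / 1.34 | 1.437 / 1.377 / 1.335 | 1.436 / 1.377 / 1.336 |
| 70% | 1.36 / 1.31 / 1.28 | 1.362 / 1.313 / 1.279 | 1.362 / 1.314 / 1.281 |

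All 18 H1d cells, including those at 90% power, fit within 0.006 under either set-up, and they fit on 112/146/180. This confirms the participant denominator.

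**Step 2: change only N, to 225, with the RR taken over all randomized PCCs.** Both set-ups give 1.39 / 1.30 / 1.25 at 30/50/70% use for 80% power, and 1.46 / 1.35 / 1.29 for 90%. The 80% range becomes about 1.25-1.39, against the printed 1.28-1.58. Put the other way, the printed 80%-power RRs have 87-98% power on 225.

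**Step 3: take the RR as the effect in trained PCCs only.** Assume that untrained PCCs show no arm effect. With participation q, the effect over all randomized PCCs is roughly q times as large, while the standard error shrinks by √(n/225). The signal ratio is q√(225/n), which is about √q because n is about 225q:

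- q = 0.50: 0.50 × √(225/112) = 0.709
- q = 0.65: 0.65 × √(225/146) = 0.807
- q = 0.80: 0.80 × √(225/180) = 0.894

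Taking the printed 80% at face value (1.96 + 0.842 = 2.802), power = Φ(2.802 × ratio − 1.96) = 51%, 62% and 71%. The two-arm Poisson formula, with the RR diluted to 1 + (RR − 1)q and T from 1 to 20 visits, gives 52-62%, 63-68% and 71-74%. Overall this is about 51-74%.

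**Step 4: H2b under the planned model.** F test of one coefficient, with stigma plus 4 covariates, noncentrality f²N, and 1 and N − 6 degrees of freedom:

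| N | 112 | 146 | 180 |
|---|---|---|---|
| f², 80% power | 0.071 | 0.055 | 0.044 |
| f², 90% power | 0.096 | 0.073 | 0.059 |

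As a check, the same test at 93% of those N (104/135/167, the non-waivered share) gives 0.077/0.059/0.048 at 80% power, which matches the printed H2a row of 0.08/0.06/0.05.

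**The case against.** The strongest reply is that H1d is defined by randomized arm and section L speaks of an effect between groups, so the RR is naturally the all-randomized effect. The larger N then only helps, and the printed row errs on the safe side. A bounded check supports this. With a per-PCC proportion on 225, an assumed between-PCC SD of 0.20-0.30 and an assumed 3.3-10 eligible visits per PCC, the detectable all-randomized RRs are about 1.30-1.44, 1.18-1.28 and 1.13-1.19 at 30/50/70% use. These meet essentially every printed 80%-power cell. The reply stands for that reading. It does not make the printed figures those of the planned test, and section L does not state the reading.

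It is also fair that a rate ratio is not wrong in itself for H1d. Section M leaves the Aim 1 link open, and a log link yields one. Requiring a bounded model would be a preference. No such defence is available for H2b, where section M names the model, although the corrected f² of 0.044-0.071 is about the size that section L calls small for H2a, so the correction is not unfavourable.

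Three stronger readings are tempting but not supported:

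- A reader might infer that the table contains an impossible value, since 0.70 × 1.43 = 1.001. This is rounding: unrounded, the cell is 1.425-1.426, or 99.8% use. It also presumes that 70% is comparison-arm use, which is not stated.
- A reader might infer that the H1d row treats arm as a continuous predictor, so that real two-arm power is near 31%. That needs exposure of one visit per PCC. An arm indicator at about 3.6 visits reproduces the row equally well, so the documents cannot settle it.
- A reader might infer that the row is definitely too optimistic at 30% use and 50% participation. In the bounded model the trained-only RR needed there is 1.60-1.90 over the assumed ranges, against the printed 1.58. With SD 0.20 and 20 visits it is 1.55, and with SD 0.15 and 10 visits it is 1.51.

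**Conclusion.** Two mismatches hold on the documents alone and should be corrected. Table 1 gives H1d sensitivity for 112/146/180 participants while the plan analyses about 225 randomized PCCs. H2b is powered with a measure that its planned model does not produce.

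The direction of the H1d error is open. On the all-randomized reading, which is closest to the hypothesis, the row is conservative (about 1.25-1.39 at 80% power). On the trained-only reading it is too optimistic (about 51-74% power); this rests on no arm effect in untrained PCCs and on accepting the printed 80%. A reader might infer that H1d is underpowered. The documents do not support that, because they nowhere define the RR as a trained-only effect. No true power for the trial is claimed here, and the d values in the summary sentence are not in question on this point.

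**What to change.** Recompute the H1d row as a 1:1 arm contrast on about 225 randomized PCCs. State:

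- whether the RR is the effect over all randomized PCCs or in trained PCCs only, with participation entered as dilution in the second case;
- the assumed number of eligible visits per PCC and the between-PCC variation;
- what 30/50/70% refers to, for example comparison-arm use;
- the G*Power procedure and inputs behind the H1d and H2b rows.

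Replace the RR range of 1.28-1.58 in the summary sentence with the result, whichever way it moves. Restate H2b as f² under the linear model, as the H2a row already does, or reconcile sections L and M by changing the planned model to one that yields a rate ratio.

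The cost is text and two table rows. Recruitment and data collection do not change, and the analysis changes only if the sponsor chooses to reconcile H2b through its model.
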